4.8.1. Adverse Events Variables

The period of safety observation starts from the time when the patient gives informed consent and continues into the following periods:

- The PRE-TREATMENT period is defined from the day the ICF is signed to the day before the first dose of double-blind study treatment administration.
- The double-blind treatment-emergent adverse event (TEAE) period is defined from the day of the first dose of double-blind study treatment administration to the day of the last dose of double-blind study treatment administration + 168 days (24 weeks) (based on PK considerations, residual effect of study treatment might be observed until 24 weeks after the last dose of study drug) for those patients not proceeding into the OLTP (ie, Group A patients and Group B patients who prematurely discontinue study treatment), or up to the day before the first dose of open-label study treatment administration for those patients proceeding into the OLTP
- The open-label treatment-emergent adverse event (TEAE) period (Group B only) is defined from the day of the first open-label study treatment administration to the day of the last open-label study treatment administration + 168 days (24 weeks).
- The POST-TREATMENT period is defined from the day after the end of the respective TEAE periods to the last study visit.

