Screening/Baseline:																	
Randomization	X																
Treatment:																	
Administer SC Study Drug ^{4, 7, 8}	X	X	X	X	X	X	X	X	X	X	X	X	X	X	X	X	
Concomitant Medications	X	X	X	X	X	X	X	X	X	X	X	X	X	X	X	X	X
Query LMT compliance	X	X	X	X	X	X	X	X	X	X	X	X	X	X	X	X	X
Safety:																	
Weight	X								X								X
Vital Signs ¹¹	X	X	X	X	X	X	X	X	X	X	X	X	X	X	X	X	X
Physical Examination																	X
Electrocardiogram ³																	X
Contraception Use Reminder ¹	X	X	X	X	X	X	X	X	X	X	X	X	X	X	X	X	X
Remind male patients to use condoms	X	X	X	X	X	X	X	X	X	X	X	X	X	X	X	X	X
Adverse Events	X	X	X	X	X	X	X	X	X	X	X	X	X	X	X	X	X
Laboratory Testing²:																	
Hematology	X		X		X				X				X				X
Chemistry	X		X		X				X				X				X
Urinalysis	X		X		X				X				X				X
Core Lipid Panel	X		X		X		X		X		X		X		X		X

	Double-Blind Treatment Period																
	Visit 2	Visit 3	Visit 4	Visit 5	Visit 6	Visit 7	Visit 8	Visit 9	Visit 10	Visit 11	Visit 12	Visit 13	Visit 14	Visit 15	Visit 16	Visit 17	Visit 18/ EOT
Day	1	8	15	22	29	36	43	50	57	64	71	78	85	92	99	106	113
Visit Window (Day)	±3	±3	±3	±3	±3	±3	±3	±3	±3	±3	±3	±3	±3	±3	±3	±3	±3
Week	0	1	2	3	4	5	6	7	8	9	10	11	12	13	14	15	16
Specialty Lipid Panel	X				X				X				X				X
HbA1c																	X
hs-CRP	X								X								X
Pregnancy Test	U				U				U				U				U
PK and Research Samples:																	
PK (evinacumab, alirocumab) ⁴ , ANGPTL3, PCSK9 sample	X	X	X		X				X		X		X				X
Anti-evinacumab antibody sample	X				X												X
Research samples (biomarkers)	X						X						X				X
LDL-R function sample ⁵	X																
[REDACTED]	X		X														
[REDACTED]	X																
Other:																	
Review of low fat diet	X	X	X	X	X	X	X	X	X	X	X	X	X	X	X	X	X

Table 4: Schedule of Events for IV Treatment Group B

	Double Blind Treatment Period									Open-Label Treatment Period					
	Visit 2	Visit 3	Visit 4	Visit 5	Visit 6	Visit 7	Visit 8	Visit 9	End of DBTP Visit 10	Visit 11	Visit 12	Visit 13	Visit 14	Visit 15	Visit 16
Day	1	15	29	43	57	85	113	141	169	197	225	253	281	309	337
Visit Window (Day)	±3	±3	±3	±3	±3	±3	±3	±3	±3	±3	±3	±3	±3	±3	±3
Week	0	2	4	6	8	12	16	20	24	28	32	36	40	44	48
Screening/Baseline:															
Randomization	X														
Treatment:															
Administer Double-Blind IV Study Drug ^{4,7}	X		X		X	X	X	X							
Administer Open-Label IV Study Drug ^{4,7}									X#	X	X	X	X	X	X
Concomitant Medications	X	X	X	X	X	X	X	X	X	X	X	X	X	X	X
Query LMT compliance	X	X	X	X	X	X	X	X	X	X	X	X	X	X	X

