8.1.1. Footnotes for the Schedule of Events Tables

EOS = end of study; EOT = end of treatment; U = urine; Core lipid panel = TC, calculated LDL-C, HDL-C, TGs, and non-HDL-C; Specialty lipid panel = ApoB, ApoA-1, ratio ApoB/ApoA-1, and Lp(a).

1. All patients will be reminded of protocol-specified contraception use and pregnancy reporting.
2. All laboratory samples should be collected before the administration of study drug. All samples should be collected following at least an 8-hour fast.
3. Electrocardiograms should be performed before blood is drawn during visits requiring blood draws.
4. On dosing days, PK collection should occur pre-dose for group A and prior to IV infusion and at the end of the IV infusion for group B.
5. LDL-R function samples will be collected from a sub-set of patients based on enrollment and will be determined by IWRS.

- [REDACTED]
- [REDACTED]
- [REDACTED]
7. For SC dosing, patients will be observed at the clinical site for at least 30 minutes following each SC study drug administration. For IV dosing, patients will be monitored for at least 60 minutes following the end of each IV study drug administration.
 8. Starting at W1 and every odd visit week (ie, W3, W5, W7, etc) thereafter, visiting home nurses may administer study drug for those patients randomized to Group A.
 9. WOCBP will be provided urine pregnancy tests with instructions to test for pregnancy at home.
 10. All subjects will be contacted by phone to query LMT compliance, inquire about AEs or changes to concomitant medications, confirm required contraception use and remind patients of pregnancy reporting. Women of childbearing potential will report the results of their home urine pregnancy test. All patients will also be queried regarding their low fat diet.
 11. Vital signs should be recorded prior to SC injection or IV infusion, and 30 minutes and 60 minutes post-IV infusion.

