5.8. Analysis of Safety Data

In general, for the double-blind period, the summary of safety results for patients in the double-blind SAF population will be presented by route of administration (Group A or Group B) and pooling the evinacumab dose regimens within each route of administration (Group A or Group B), with the intent to maximize efforts to identify potential safety signals. The treatment group data (individual evinacumab dose regimens and placebo) will also be presented with the intent to support the pooled dose regimens. No formal inferential testing will be performed. Summaries will be descriptive in nature.

For Group B, summaries of safety results for the open-label period will be presented for patients in the open-label SAF, by the total number of patients administered open-label study treatment (i.e., 15 mg/kg IV), as well as by the patient subgroups of study treatment received in the DBTP (i.e., 5 mg/kg IV, 15 mg/kg IV, or placebo). Summaries will be descriptive in nature.

General common rules

All safety analyses will be performed, unless otherwise specified, using the following common rules:

- For DBTP, safety data in patients who do not belong to the double-blind safety analysis set (i.e., exposed but not randomized) will be listed separately.
- PCSV values are defined as abnormal values considered medically important by the Sponsor according to predefined criteria/thresholds based on literature review and defined by the Sponsor for clinical laboratory tests and vital signs (PCSV version dated January 2009 [[Appendix 10.4](#)]). Considering that the threshold defined in the PCSV list for monocytes and basophils can be below the ULN, the following PCSV criterion will be used for the PCSV analysis of monocytes and basophils:
 - PCSV criterion for monocytes: >0.7 Giga/L or $>ULN$ (if $ULN \geq 0.7$ Giga/L).
 - PCSV criterion for basophils: >0.1 Giga/L or $>ULN$ (if $ULN \geq 0.1$ Giga/L).
- PCSV criteria will determine which patients had at least 1 PCSV during the respective TEAE periods, taking into account all evaluations including unscheduled or repeated evaluations.
- The treatment-emergent PCSV denominator by treatment group for a given parameter will be based on the number of patients assessed for that given parameter at least once during the respective TEAE periods.

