5.8.3. Clinical Laboratory Measurements

The following definitions will be applied to laboratory parameters:

- Double-blind treatment period: The treatment period used for quantitative analysis in the double-blind period is defined as the day after the first study drug administration to the day of the last double-blind study drug injection + 7 days for Group A. For Group B, the treatment period is defined from the day after the first administration of double-blind study treatment to the day of the last administration of double-blind study treatment + 28 days for those patients not proceeding into the open-label treatment period, or up to the day of the first open-label study treatment administration for those patients proceeding into the open-label treatment period.
- Open-label treatment period: The treatment period used for quantitative analysis in the open-label study period is defined from the day after the first dose of open-label study treatment to the day of the last dose of open label study treatment + 28 days.

For respective treatment period (DBTP and OLTP), clinical laboratory parameter actual values (quantitative) and change from baseline values will be descriptively summarized at baseline and each post-baseline visit by at least patient number, mean, median, Q1, Q3, SD, minimum and maximum. Clinical laboratory parameters mean changes from baseline, with the corresponding SE, can be plotted at each visit in the case results warrant further investigation. These parameters will be presented by the biological functions defined in Section 4.8.2. For glucose, only fasting samples will be included in the summaries.

Individual patient laboratory parameter measurements will be additionally evaluated by PCSV criteria (See Appendix 10.4), specifically identifying patients with at least one post-baseline measurement that meets the PCSV criteria within the respective TEAE periods. These laboratory parameters will be presented by the biological functions defined in Section 4.8.2. The incidence of PCSVs at any time during the respective TEAE periods will be summarized regardless of the baseline level, and again according to the following baseline categories:

- Normal (according to PCSV criterion/criteria)/missing
- Abnormal according to PCSV criterion or criteria

Patient listings of laboratory measurements that meet PCSV criteria will be provided for the report appendix. For those laboratory parameters that don't have an associated PCSV criteria,

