5.8.5. Analysis of 12-Lead ECG

The following definitions will be applied to ECG parameters:

- **Double-blind treatment period:** The treatment period used for quantitative analysis in the double-blind period is defined as the day after the first study drug administration to the day of the last double-blind study drug injection + 7 days for Group A. For Group B, the treatment period is defined from the day after the first administration of double-blind study treatment to the day of the last administration of double-blind study treatment + 28 days for those patients not proceeding into the open-label treatment period, or up to the day of the first open-label study treatment administration for those patients proceeding into the open-label treatment period.
- **Open-label treatment period:** The treatment period used for quantitative analysis in the open-label study period is defined from the day after the first dose of open-label study treatment to the day of the last dose of open label study treatment + 28 days.

For respective treatment period (DBTP and OLTP), ECG parameters will be described through an overall interpretation of ECG status (e.g. normal, abnormal [clinically significant (Yes/No)]). The count and percentage of patients with at least 1 abnormal post-baseline ECG during the respective TEAE period will be summarized according to the following baseline status categories:

- Normal/missing;
- Abnormal

Individual patient ECG measurements will be additionally evaluated by PCSV criteria, specifically identifying patients with at least one post-baseline measurement that meets the PCSV criteria within the TEAE period. The incidence of PCSVs at any time during the respective TEAE periods will be summarized regardless of the baseline level, and again according to the following baseline categories:

- Normal (according to PCSV criterion/criteria)/missing
- Abnormal according to PCSV criterion or criteria

Patient listings of ECG measurements that meet PCSV criteria will be provided for the report appendix.

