10.2. Windows for Analysis Time Points

Below are the definitions for the visit windows programmatically imposed on measures repeatedly collected over the course of the study. These visit windows reflect the study schedule of assessments as described in the protocol.

The visit windows are constructed using ranges applied to the number of days in study (study days) when the measure is collected. Below are the relevant definitions for the analysis visit windows:

1. Study day is defined as the number of days since the first study treatment administration +1. The first study treatment occurs on Study Day 1.
2. Open-label study day is defined as the number of days since the first open-label study treatment administration+1
3. Since the protocol specifies that measurements be collected before study treatment is administered on a given day, it is appropriate that baseline include Day 1.
4. For randomized but not treated patients, Day 1 is the day of randomization.

Table 1 Global Analysis Windows for Group B (IV)

Visit label	Targeted Study Day	Targeted Open-Label Study Day	Analysis Window in Study Day
Screening	< Day 1	N/A	Measurement obtained prior to first study treatment, and not defined as baseline visit
Baseline	1	N/A	Measurement obtained closest to first study treatment, while remaining prior to first study treatment
Week 2	15	N/A	2 to 21
Week 4	29	N/A	22 to 35
Week 6	43	N/A	36 to 49
Week 8	57	N/A	50 to 70
Week 12	85	N/A	71 to 98
Week 16	113	N/A	99 to 128
Week 20	141	N/A	129 to 154
Week 24	169	Day 1	155 to 182
Week 28	197	29	183 to 210
Week 32	225	57	211 to 238
Week 36	253	85	239 to 266
Week 40	281	113	267 to 294
Week 44	309	141	295 to 322

Visit label	Targeted Study Day	Targeted Open-Label Study Day	Analysis Window in Study Day
Week 48	337	169	323 to 350
Week 52	365	197	351 to 378
Week 56	393	225	379 to 406
Week 60	421	253	407 to 434
Week 64	449	281	435 to 462
Week 68	477	309	463 to 490
Week 72	505	337	491 to 518
FU – W4	For patients prematurely discontinued trt: last study trt + 28 days For patients completed OLTP: 533	For patients prematurely discontinued trt: last study trt + 28 days For patients completed OLTP: 365	For patients prematurely discontinued trt: last study trt to 56 days after last study trt For patients completed OLTP: 519 to 560

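### In Group B, abnormal-ECG, PCSV and eDISH counts assign pre-dose week-24 assessments to the open-label period, which removes the only scheduled post-baseline double-blind ECG for patients dosed that day

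*SAP*

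**What the plan says.** **TEAE periods.** For Group B patients who go on to open-label treatment, SAP 4.8.1 ends the double-blind TEAE period with the wording "or up to the day before the first dose of open-label study treatment administration for those patients proceeding into the OLTP". Its open-label counterpart reads: "is defined from the day of the first open-label study treatment administration to the day of the last open-label study treatment administration + 168 days". Protocol 10.4.4.1 gives the same rule. Neither document splits the first open-label dosing day into before and after the infusion.

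**Where these periods are used.** SAP 5.8 states that "PCSV criteria will determine which patients had at least 1 PCSV during the respective TEAE periods", and takes as the PCSV denominator the patients assessed for the parameter in that period. SAP 5.8.5 counts "patients with at least 1 abnormal post-baseline ECG during the respective TEAE period". The eDISH plot in SAP 5.8.3 also uses post-baseline values in the TEAE periods.

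**A second period rule.** For by-visit summaries, SAP 5.8.3, 5.8.4 and 5.8.5 define a double-blind treatment period that runs "or up to the day of the first open-label study treatment administration for those patients proceeding into the open-label treatment period". Its open-label counterpart starts the day after that dose.

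**The visit itself.** In Protocol Table 4, the column headed "End of DBTP Visit 10" (day 169) carries the first open-label infusion. SAP Appendix 10.2, Table 1 equates the two days: "Week 24 169 Day 1 155 to 182". Protocol 8.1.1, footnote 2, says "All laboratory samples should be collected before the administration of study drug"; footnote 3 places the ECG before the blood draw; footnote 11 asks for vital signs before the infusion and 30 and 60 minutes after it.

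**The concern.** Pre-dose results at week 24 reflect randomised treatment only. The TEAE rule works in whole days, which is a usual convention for AE onset dates. It does not suit measurements that the protocol requires before the infusion on that same day. SAP 4.8 keeps the double-blind baseline for both periods, so a week-24 value is not absorbed as an open-label baseline. It becomes a post-baseline open-label finding.

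Two things are at stake. First, Table 4 schedules only one post-baseline ECG during double-blind treatment, at week 24. If it moves, the randomised comparison of abnormal-ECG and ECG-PCSV incidence in Group B rests mainly on patients who stopped early or started open-label late. Second, an abnormality that arose on placebo or on 5 mg/kg is tabulated as a finding under open-label 15 mg/kg.

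**Working it through.** **Inputs.** Visit days and assessment marks come from Protocol Table 4. Period rules come from SAP 4.8.1 and 5.8.3-5.8.5. Group B has 108 patients, 72 on evinacumab and 36 on placebo (Protocol 6.1). The 5% dropout comes from Protocol 10.2 and SAP 2.2.

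**Step 1: the day.** Week 24 is study day 24 × 7 + 1 = 169, which reproduces the SAP's day 169 and open-label Day 1. The last double-blind infusion, at week 20, is on day 20 × 7 + 1 = 141.

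**Step 2: the two rules for a patient dosed open-label on day 169.**
- TEAE rule: double-blind through day 168; open-label from day 169.
- By-visit rule: double-blind through day 169; open-label from day 170.

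The same day-169 sample is therefore open-label in a PCSV table and double-blind in a by-visit table.

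**Step 3: scheduled post-baseline double-blind visits under each rule.**

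| Assessment | Weeks scheduled | Total | TEAE rule (day ≤ 168) | By-visit rule (day ≤ 169) |
|---|---|---|---|---|
| ECG | 24 | 1 | 0 | 1 |
| Haematology, chemistry, urinalysis | 2, 4, 8, 12, 16, 20, 24 | 7 | 6 | 7 |
| HbA1c | 12, 24 | 2 | 1 | 2 |
| Vital signs (visits) | 2, 4, 6, 8, 12, 16, 20, 24 | 8 | 7 | 8 |

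The vital-sign row overstates the loss. Footnote 11 adds two post-infusion readings at each of six double-blind infusions. There are thus 8 + 6 × 2 = 20 scheduled post-baseline sets, and 1 of 20 (the week-24 pre-dose set) is displaced.

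**Step 4: who still supplies a double-blind ECG.** If everyone who continues is dosed on the week-24 visit day, only patients who do not continue have a scheduled ECG in the double-blind TEAE period. The documents give no non-entry rate, so the 5% dropout is used as a proxy.

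| Non-entry (assumed) | Group B, of 108 | Evinacumab, of 72 | Placebo, of 36 |
|---|---|---|---|
| 0% | 0 | 0 | 0 |
| 5% | 108 × 0.05 = 5.4 | 3.6 | 1.8 |
| 20% | 108 × 0.20 = 21.6 | 14.4 | 7.2 |

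**Step 5: HbA1c and new-onset diabetes.** The HbA1c criterion in SAP Appendix 10.3 needs two values of at least 6.5% in the TEAE period, but accepts one if it is the only value or the last of several. With week 24 moved, week 12 is the only scheduled double-blind value. A patient high at week 12 and normal at week 24 becomes a double-blind case by this criterion. A patient normal at week 12 and high at week 24 is no longer one.

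**Group A.** The last dose is at week 15, day 15 × 7 + 1 = 106. The week-16 ECG on day 113 lies well inside last dose + 168 days, so Group A is not affected.

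**The case against.** The strongest case on the other side is that the defect is narrow and that several broader readings fail. Much of this stands.

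- **A reader might infer that week 24 drops out of the double-blind safety analysis altogether.** It does not. The by-visit laboratory and vital-sign summaries include the day of the first open-label dose, and week 24 has its own analysis window. SAP 5.8.5 also uses the by-visit period when it describes overall ECG status. Only the incidence counts are affected. hs-CRP is summarised by visit over the treatment period (SAP 5.9), so no loss is claimed for it.
- **A reader might infer that every continuing patient loses the ECG.** That is an upper bound. The week-24 open-label dose mark carries a symbol with no explanation in the available text. SAP 5.7.2.5 foresees some long gaps before open-label dosing, and Protocol 7.1 allows a 14-day margin for infusions. A week-24 ECG on a day before the open-label dose stays double-blind. Unscheduled ECGs also count.
- **A reader might infer that placebo abnormalities vanish into one evinacumab total.** SAP 5.8 also presents open-label safety by double-blind arm, and PCSV measurements are listed by patient. The misplacement can be seen, but it still sits in the wrong period.
- **Laboratory and vital-sign counts are any-time or peak measures.** They change only where an abnormality first appears, or peaks, at week 24.
- **Safety is descriptive.** No inferential test is planned for it, and neither efficacy nor the AE onset rule is in question.

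None of this restores the abnormal-ECG and ECG-PCSV counts. The assessed-patient denominator is explicit only for PCSVs. If the abnormal-ECG percentage used the whole safety set instead, it would be artificially low rather than based on few patients.

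**Conclusion.** The point holds for the Group B abnormal-ECG, PCSV and eDISH counts. As written, pre-dose week-24 assessments count as open-label for any patient whose first open-label infusion falls on that visit day, and this contradicts the SAP's by-visit rule for the same day. The effect is serious for ECG (0 of 1 scheduled double-blind assessments remains) and moderate for HbA1c (1 of 2). It is small for other laboratory counts (6 of 7 visits remain) and for vital signs (one pre-dose set lost).

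About 5 of 108 patients would be non-continuers still able to supply a scheduled double-blind ECG, with a range of 0 to about 22. This rests on two assumptions: non-entry of 5% (range 0-20%), and same-day dosing for all who continue. Late starters would raise the number, and the documents do not say how many to expect. Because these tables are descriptive and most laboratory and vital-sign data stay in place, this is a should-fix.

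**What to change.** Add a common rule to SAP 5.8, carry it into 5.8.3-5.8.5, and mirror it in Protocol 10.4.4.2. For Group B patients entering open-label treatment, assessments taken before the infusion on the day of the first open-label dose belong to the double-blind period for abnormal-ECG, PCSV and eDISH counts and for the laboratory-based AESI criteria in Appendix 10.3. Open-label assessments start after that infusion. SAP Appendix 10.2 already reasons this way at study entry, where Day 1 values count as baseline because sampling precedes dosing.

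For laboratory samples and ECGs without a recorded time, the protocol's required order settles the assignment. It cannot do so for vital signs, which are taken before and after the infusion, so those need the recorded time or the pre-/post-infusion timepoint label. The 30- and 60-minute readings stay open-label. Leave the AE onset-date rule as it is.

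The cost is a few sentences and one programming condition, with no new data. At 5% non-entry, about 108 − 5.4 = 102.6, or 103 patients, would regain their only scheduled double-blind ECG (108 at 0% non-entry, about 86 at 20%), again assuming same-day dosing.
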